4.2. TREATMENT PHASE

Subjects who meet all eligibility criteria, as per data gathered from Screening Period are to be treated. All subjects who fail to meet eligibility criteria will be considered screen failure and will exit the study without further evaluation

4.2.1. Visit 2 (V2)

The following assessments will be performed at the first treatment visit prior to the first treatment administration. If Visit 2 (V2) takes place on the same day as the Screening Visit (V1), scheduled assessments performed under screening (V1) do not need to be repeated at V2.

- Physical examination (see Section 7.5);
- Vital Signs (see Section 7.6),
- Clinical Status Ordinal scale assessment (see Section 7.10);
- PaO2/FiO2, if intubated (See Section 7.11)
- Pulse oxygen saturation (SpO2) (see Section 7.12);
- Positive End-Expiratory Pressure (PEEP), if intubated (See Section 7.13)
- Sequential Organ Failure Assessment (SOFA) score, if intubated (See Section 7.14)

CONFIDENTIAL Page 55 of 108

National Early Warning Score 2 (NEWS2) Assessment (see Section 7.15);

- Collection of blood specimens (see Section 7.8) for
 - o CD3+, CD4+ and CD8+ T cell count;
 - o CCR5 receptor occupancy for Treg and macrophage;
 - o Serum cytokine and chemokine levels; and
 - o CCR5 Gene Polymorphisms.
- Nasopharyngeal Swab Sample Collection (See Section 7.18)
- Assessment for the requirement of mechanical ventilation, Non-Invasive Ventilation, Supplemental Oxygen, Vasopressors Use, Renal Replacement Therapy, ICU Admission, and hospital stay (see Section 7.20);
- Assessment for any new infections; and
- Prior medications assessment (see Section 7.7).

Subjects will be randomized 2:1 via WebView CTMS system to Leronlimab (PRO 140) or Placebo (see Section 7.21).

- Leronlimab (PRO 140) 700 mg or
- Placebo

Note: In the single arm, non-randomized, open-label phase, all eligible subjects will be assigned to receive Leronlimab (PRO 140).

Leronlimab (PRO 140) or placebo will be administered subcutaneously to all subjects at a weekly dose of 700 mg. After receiving the first leronlimab (PRO 140) dose, the following assessments will be performed:

- Vital signs (see Section 7.6),
- Concomitant medications assessment (see Section 7.7),
- Review of adverse events (see Section 9)

4.2.2. Visits 3 and 4, (V3 and V4)

The following assessments will be performed during the remaining visits during the treatment period:

- Physical examination (see Section 7.5);
- Vital Signs (see Section 7.6),

CONFIDENTIAL Page 56 of 108

Date: 28-Dec-2020

- Clinical Status Ordinal scale assessment (see Section 7.10);
- PaO2/FiO2, if intubated (See Section 7.11)
- Pulse oxygen saturation (SpO2) (see Section 7.12);
- Positive End-Expiratory Pressure (PEEP), if intubated (See Section 7.13)
- Sequential Organ Failure Assessment (SOFA) score, if intubated (See Section 7.14)
- National Early Warning Score 2 (NEWS2) assessment (see Section 7.15)
- Assessment of Clinical Recovery (See Section 7.16)
- Collection of blood specimens (see Section 7.8) for
 - Complete blood count;
 - Biochemistry;
 - Coagulation indices;
 - Urine sample for urinalysis parameters;
 - CD3+, CD4+ and CD8+ T cell count;
 - CCR5 receptor occupancy for Treg and macrophage;
 - Serum cytokine and chemokine levels; and
 - CCR5 Gene Polymorphisms
- Nasopharyngeal Swab Sample Collection (See Section 7.18)
- Leronlimab (PRO 140) or Placebo Administration V4 only (see Section 6.1.3);
- Assessment for the requirement of mechanical ventilation, Non-Invasive Ventilation, Supplemental Oxygen, Vasopressors Use, Renal Replacement Therapy, ICU Admission, and hospital stay (see Section 7.20);
- Assessment for any new infections;
- Prior medications assessment (see Section 7.7); and
- Review of adverse events (see Section 9).

4.2.3. End of Treatment – EOT (V5)

The last visit during the treatment phase will be considered at the End of Treatment (EOT) visit. The assessments performed at this visit will include:

Physical examination (see Section 7.5);

CONFIDENTIAL Page 57 of 108

- Vital Signs (see Section 7.6),
- Clinical Status Ordinal scale assessment (see Section 7.10);
- PaO2/FiO2, if intubated (See Section 7.11)
- Pulse oxygen saturation (SpO2) (see Section 7.12);
- Positive End-Expiratory Pressure (PEEP), if intubated (See Section 7.13)
- Sequential Organ Failure Assessment (SOFA) score, if intubated (See Section 7.14)
- National Early Warning Score 2 (NEWS2) assessment (see Section 7.15);
- Assessment of Clinical Recovery (See Section 7.16)
- 12-lead electrocardiogram (see Section 7.17);
- Collection of blood specimens (see Section 7.8) for
 - Complete blood count;
 - Biochemistry;
 - Coagulation indices;
 - o Serum/urine pregnancy test, for female subjects of childbearing potential;
 - Urine sample for urinalysis parameters;
 - o CD3+, CD4+ and CD8+ T cell count;
 - o CCR5 receptor occupancy for Treg and macrophage;
 - o Serum cytokine and chemokine levels; and
 - o CCR5 Gene Polymorphisms.
- Nasopharyngeal Swab Sample Collection (See Section 7.18)
- Chest radiograph or computer tomography (CT) scan (if clinically indicated) (See Section 7.19);
- Assessment for the requirement of mechanical ventilation, Non-Invasive Ventilation, Supplemental Oxygen, Vasopressors Use, Renal Replacement Therapy, ICU Admission, and hospital stay (see Section 7.20);
- Assessment for any new infections;
- Review of mortality status;
- Prior medications assessment (see Section 7.7); and

CONFIDENTIAL Page 58 of 108

Review of adverse events (see Section 9).

4.3. FOLLOW-UP PHASE

The first visit of the follow-up phase is scheduled 14(±3) days after EOT Visit. Two follow-up visits are included in the follow-up phase.

4.3.1. Visits 6 and 7 (V6 and V7)

The assessments performed at these visits will include:

[figure not shown]
- Physical examination (see Section 7.5);
- Vital Signs (see Section 7.6),
- Clinical Status Ordinal scale assessment at Visit 6 only (see Section 7.10);
- Collection of blood specimens at Visit 7 only (see Section 7.8) for
 - Complete blood count;
 - Biochemistry;
 - Coagulation indices; and
 - Urine sample for urinalysis parameters.
- Nasopharyngeal Swab Sample Collection (See Section 7.18)
- Review of mortality status;
- Prior medications assessment (see Section 7.7); and
- Review of adverse events (see Section 9).

Note: The follow-up visits (V6 and V7) can be conducted as telephone or video contact visits. If V7 is a telephone/video visit, the scheduled blood sample collection will not be performed. In such cases, missed blood sample collection will not be captured as protocol deviation.

The following assessments are not applicable for the single arm, non-randomized, open-label phase of the study:

- National Early Warning Score 2 (NEWS2) Assessment
- Blood sample collection for
 - CCR5 receptor occupancy for Treg and macrophage
 - Serum cytokine and chemokine levels
 - CCR5 Gene Polymorphisms
- Nasopharyngeal Swab Sample Collection

CONFIDENTIAL Page 59 of 108

4.4. UNSCHEDULED VISITS

In the event that the subject will return to clinic at a time other than a regularly scheduled study visit, the visit will be regarded as an unscheduled visit. Assessments at unscheduled visits are at the discretion of the Investigator. All pertinent findings, including adverse events or changes in medications, will be noted in the eCRF.

CONFIDENTIAL Page 60 of 108

Date: 28-Dec-2020

5. SUBJECT COMPLETION, WITHDRAWAL AND CRITERIA FOR STOPPING THE STUDY

5.1. **SUBJECT COMPLETION**

A subject is considered to have completed the study once all follow-up visit assessments have been completed.

5.2. EARLY STOPPING RULES

Upon occurrence of any of the following events, data will be reviewed by the Medical Monitor and the Lead Principal Investigator.

- 1. Death in any subject in which the cause of death is judged to be probably or definitely related to the study drug by the treating investigator;
- 2. The occurrence in any subject of a life-threatening SAE whose causal relationship to study drug is judged to be probable or definite by the treating investigator;
- 3. Two (2) occurrences of Grade 4 toxicities that are assessed to be probably or definitely related to the study drug by the treating investigator;
- 4. Two (2) occurrences of a Grade 2 or higher allergic/hypersensitivity reaction directly related to the study drug that lead to permanent discontinuation of study drug.

In case the above listed event(s) occurred, patient accrual will be suspended pending further review and the FDA and other global regulatory authority will be notified. The study will be stopped if any of these stopping criteria are met unless, after reviewing the safety events of interest, the medical monitor and Sponsor, agree to allow the study to proceed. The FDA and other global regulatory authority will be consulted for any protocol amendment before restarting the trial if a stopping rule is met.

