Subjects who meet the eligibility criteria will have completed the following evaluations and assessments at V2 prior to treatment: review of any changes in medical and medication history, physical examination, vital signs, clinical status – ordinal scale assessment, PaO2/FiO2 measurement, pulse oxygen saturation (SpO2), positive end-expiratory pressure (PEEP) (for intubated subjects), sequential Organ Failure Assessment (SOFA) score, National Early Warning Score 2 (NEWS2) assessment, nasopharyngeal swab sample collection, baseline assessment for the requirement of: mechanical ventilation, non-invasive ventilation, supplemental oxygen, vasopressors use, renal replacement therapy, ICU admission and hospital stay, assessment for any new infections, blood sample collection for CD3+, CD4+ and CD8+ T cell count, CCR5 receptor occupancy for Treg and macrophages, serum cytokine and chemokine levels, and CCR5 gene polymorphisms. After administration of leronlimab subjects will be assessed for vital sign, adverse event and concomitant medications. If Visit 2 (V2) takes place on the same day as the Screening

CONFIDENTIAL Page 48 of 108

Visit (V1), scheduled assessments performed under screening (V1) do not need to be repeated at V2.

Table 4-1: Treatment Groups

Study Drug	Dosage Form	IP concentration	Dosing Frequency and Amount	Route of Administration
PRO 140 (700 mg)	Parenteral solution	175 mg/mL	2 injections of PRO 140 (2 X 2 mL/inj.) per week on opposite sides of abdomen	SC injection
Placebo	Parenteral solution	0 mg/mL	2 injections of placebo (2 X 2 mL/inj.) per week on opposite sides of abdomen	SC injection

At V2, subjects will be randomized to receive leronlimab (PRO 140) or placebo which will be administered subcutaneously weekly at Visit 2 (Day 0) and Visit 4 (Day 7) by a qualified medical professional at clinic. If the subject is discharged from the hospital prior to Visit 7 (Day 42), the visit can be completed at the subject's home.

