6. STUDY TREATMENT

Leronlimab (PRO 140) or placebo will be administered subcutaneously (SC) at a weekly as follows:

Table 6-1: Treatment Administration Summary

Study Drug	Dose	Route	Schedule
Leronlimab (PRO 140)	$700~\mathrm{mg}$	SC	Weekly (2 doses)
Placebo	$0~\mathrm{mg}$	SC	Weekly (2 doses)

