6.1.5. Leronlimab (PRO 140) - Toxicity Management

Refer to Table 6-3 and Table 6-4

Table 6-4below. Recovery to acceptable levels must occur to allow leronlimab (PRO 140) continuation.

Table 6-3: Leronlimab (PRO 140) - Management for Injection Site Reactions

CTCAE Grade	Treatment Management
Grade 1	No dose adjustment is required.
Grade 2	First Occurrence: No dose adjustment is required. Second Occurrence of the same event: Closely follow-up for resolution of the AE to Grade ≤ 1
Grade 3	Withhold treatment until symptoms resolve to: • Grade 1 or less
Grade 4	Study treatment will be permanently discontinued

CONFIDENTIAL Page 66 of 108

Table 6-4: Leronlimab (PRO 140) - Management for all Other Potential Toxicities

CTCAE Grade (attributable to leronlimab)	Treatment Management
Grade 1	No dose adjustment is required.
Grade 2	Withhold treatment until symptoms resolve to: • Grade 1 or less or baseline;
Grade 3	Study treatment will be permanently discontinued
Grade 4	Study treatment will be permanently discontinued

(Attributable to Leronlimab)

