9.2.2. CTCAE Grade (Intensity) Assessment

The guidelines outlined in CTCAE v5.0 will be used for assessing the intensity of the event (See Appendix 17.2). The general guidelines for assessing the AE grade appear below. Full guidelines may be obtained at

CONFIDENTIAL Page 85 of 108

Grade 4

Grade 5

https://ctep.cancer.gov/protocolDevelopment/electronic applications/docs/CTCAE v5 Quick Re ference 8.5x11.pdf

Grade Description Grade 1 Mild; asymptomatic or mild symptoms; clinical or diagnostic observations only; intervention not indicated. Grade 2 Moderate; minimal, local or noninvasive intervention indicated; limiting ageappropriate instrumental activities of daily living (ADL)*. Grade 3 Severe or medically significant but not immediately life-threatening; hospitalization or prolongation of hospitalization indicated; disabling; limiting self care ADL†.

Table 9-1: CTCAE v5.0 General Guidelines

Life-threatening consequences; urgent intervention indicated.

-Common Terminology Criteria for Adverse Events (CTCAE), v5.0: November 27, 2017

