9.3. SERIOUS ADVERSE EVENTS

A SAE is defined as any AE that:

- Results in death
- Is life threatening (the subject is at immediate risk of dying from the adverse experience)
- Requires subject's hospitalization or prolongs existing hospitalization
- Results in persistent or significant disability/incapacity
- Is a congenital anomaly/birth defect

CONFIDENTIAL Page 87 of 108

Important medical events that may not result in death, be life-threatening, or require hospitalization may be considered a serious adverse effect when, based upon appropriate medical judgment, they may jeopardize the subject or subject and may require medical or

surgical intervention to prevent one of the outcomes listed in this definition.

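### Stopping rule 4 counts a hypersensitivity reaction only if it leads to permanent discontinuation, so its wording leaves out or leaves unclear a related Grade 3 reaction after the second and last dose

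*Protocol*

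**What the plan says.** Protocol 5.2 lists four triggers. If one is met, "patient accrual will be suspended pending further review", and regulators are notified. The study may proceed if the medical monitor and sponsor agree after review.

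- Rule 1: one death judged probably or definitely related to study drug.
- Rule 2: one life-threatening SAE with the same causality.
- Rule 3: "Two (2) occurrences of Grade 4 toxicities that are assessed to be probably or definitely related to the study drug".
- Rule 4: "Two (2) occurrences of a Grade 2 or higher allergic/hypersensitivity reaction directly related to the study drug that lead to permanent discontinuation".

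The provisions that decide how rule 4 works are elsewhere:

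- Section 4 and Table 6-1: two weekly doses, at Visit 2 (Day 0) and Visit 4 (Day 7).
- Table 6-4 (toxicities other than injection-site reactions): for attributable Grade 3 or 4, "Study treatment will be permanently discontinued". For Grade 2, treatment is only withheld until recovery.
- Section 5.3: attributable Grade 3 or 4 toxicity is among the listed reasons for removal from treatment or study.
- Section 9.2.1: each adverse event gets an action code such as 'drug withdrawn' or 'dose not changed'. The code 'not applicable' is reserved for subjects who have left the Treatment Phase, which ends at the EOT visit (4.2.3).
- Section 9.2: adverse events are collected to the final visit, nominally Day 42.

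**The concern.** The trigger depends on a consequence of the reaction as well as on its severity and cause. With two doses, that consequence is plainly available only after the first. Two related Grade 3 reactions after dose 1 suspend accrual. The same two after dose 2, on re-exposure to the antibody, may not.

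Allergic reaction is the first risk named in Protocol 1.6, and the same section says recipients can develop an immune response to the antibody. Reactions on re-exposure are therefore a natural thing for this rule to count. What is at stake is whether an automatic pause and review happens. No efficacy estimate or test is involved.

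**Working it through.** The plan gives no operating figure for its stopping rules, so there is none to reproduce. The check is of wording, followed by a count and an illustration.

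**Step 1: do rules 1 to 3 reach the event?** The event is a related Grade 3 hypersensitivity reaction, not at the injection site, after dose 2. It is not a death (rule 1) and not Grade 4 (rule 3). Table 9-1 defines Grade 3 as "Severe or medically significant but not immediately life-threatening", while section 9.3 defines life-threatening as meaning "the subject is at immediate risk of dying from the adverse experience". A reaction correctly graded 3 therefore does not meet rule 2.

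**Step 2: does rule 4 reach it?**

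| Onset of the Grade 3 reaction | Literal wording | Reading through Table 6-4 and 5.3 |
|---|---|---|
| After dose 1, before dose 2 | counts | counts |
| After dose 2, up to EOT (nominally Day 7 to 14) | does not count | counts |
| After EOT (nominally Day 14 to 42) | does not count | arguable, but the action code can be 'not applicable' |

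Adverse events are collected for a nominal 42 − 7 = 35 days after the last dose: 14 − 7 = 7 before EOT and 42 − 14 = 28 after it. These are lengths of time, not shares of risk. If reactions cluster soon after injection (an assumption), most would fall in the ambiguous middle row. Later onset cannot be dismissed. Section 1.4.1 gives a half-life of about 200 hours in monkeys, and nominal EOT is 7 × 24 = 168 hours after the last dose. If human kinetics are similar, exposure continues past EOT.

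**Step 3: timing patterns.** Rule 4 needs two occurrences. Take two such reactions in two subjects.

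| Pattern | Literal count | Triggers? | Count under broader reading | Triggers? |
|---|---|---|---|---|
| both after dose 1 | 1 + 1 = 2 | yes | 2 | yes |
| one after each dose | 1 + 0 = 1 | no | 2 | yes |
| both after dose 2 | 0 + 0 = 0 | no | 2 | yes |

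The literal rule triggers in 1 of 3 patterns and the broader reading in 3 of 3.

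**Step 4: illustration with assumed rates.** The documents give no rate for this event, so the per-dose probability q is an assumption. Take n = 100 open-label subjects, two doses each and a count starting at zero. The chance of at least two countable events is 1 − (1 − p)^n − n·p·(1 − p)^(n − 1). Use p = q if only dose 1 counts, and p = 1 − (1 − q)² if either dose counts. For q = 0.2%, dose 1 only: 1 − 0.8186 − 0.1640 = 0.0174. With either dose, p = 1 − 0.998² = 0.003996, which gives 0.0611.

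| Assumed q per dose | Only dose 1 counts | Either dose counts |
|---|---|---|
| 0.1% | 0.5% | 1.7% |
| 0.2% | 1.7% | 6.1% |
| 0.5% | 9.0% | 26.3% |
| 1% | 26.4% | 59.4% |

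The second column treats every dose 2 reaction as missed, so at each assumed rate the difference between the columns is the most the gap could cost.

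**The case against.** The strongest reply is that the protocol, read as a whole, already counts these reactions. Table 6-4 prescribes permanent discontinuation for attributable Grade 3 toxicity without limiting it to the first dose. Section 5.3 has no dose limit either. Because 9.2.1 reserves 'not applicable' for subjects outside the Treatment Phase, a reaction between Day 7 and EOT still needs an action code although no dose is due, and 'drug withdrawn' is a reasonable choice. This stands as a fair reading for that interval. It does not settle the matter: 'dose not changed' is also available, and nothing in 5.2 says that a discontinuation with no dose remaining satisfies rule 4. After EOT the coding argument falls away.

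The second reply is that oversight continues without rule 4. SAEs reach the Medical Monitor within 24 hours (9.4), and a Grade 3 reaction that prolongs hospitalization is an SAE. Removal of one subject from the study for safety triggers regulator notification (5.3). The Data Safety Monitoring Committee (DSMC) can meet ad hoc (Protocol 12) and can recommend stopping at any time (SAP 5.1.6). All this stands and limits the severity, but none of it suspends accrual automatically. The safety reviews scheduled in SAP 5.1 are for randomized subjects, so the SAP schedules none for the open-label phase; the DSMC charter may do so.

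The third reply is that the events are rare. Section 1.6 reports no anaphylaxis in prior trials. Section 1.5.2 reports that, among 131 subjects given 700 mg, all definitely related events were mild or moderate injection-site reactions. This also stands.

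**Conclusion.** The point holds as a minor wording gap. Rule 4 does not say whether a related, non-life-threatening Grade 3 hypersensitivity reaction after the last dose counts. On the literal wording it does not. Up to EOT the text supports either reading; after EOT the gap is clearest. The size is 1 of 3 against 3 of 3 timing patterns, with no claim about frequency.

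A reader might infer that the trial has no protection against hypersensitivity after dose 2. The documents do not support that: related deaths, life-threatening SAEs and Grade 4 toxicities are covered by rules 1 to 3 after either dose, and the other oversight remains. A reader might also infer that every reaction after Day 7 is certainly missed. That goes too far, because of Table 6-4, 5.3 and 9.2.1.

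The consequence is narrow. Protocol 3 and 8.3 place the open-label phase after completion of randomized enrollment. On the assumption that this enrollment is complete, a pause would bear mainly on about 100 open-label subjects. The conclusion also assumes that reactions are graded as Table 9-1 defines and excludes injection-site reactions, which follow Table 6-3.

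**What to change.** Reword rule 4 along these lines: *two occurrences of an allergic or hypersensitivity reaction of Grade 2 or higher, judged probably or definitely related by the treating investigator, that lead to permanent discontinuation, or that would have required it under Table 6-4 had a further dose been due.*

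The causality terms are those of rules 1 to 3. The current term, directly related, is not one of the five categories in 9.2.3. If the sponsor meant only definite relation, this part widens the rule, and the sponsor should confirm the intent.

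One asymmetry remains. A Grade 2 reaction after dose 1 counts if the investigator chooses to stop treatment, while a Grade 2 reaction after dose 2 does not count, because Table 6-4 only withholds treatment at that grade. That seems acceptable, since the added clause follows the protocol's own discontinuation threshold.

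The cost is one sentence in 5.2. Grade, causality and onset date are already recorded for every adverse event (9.2), so no new data are needed. The downside is that review and a temporary accrual pause may be triggered slightly more often; 5.2 already allows the study to proceed after review.

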8.6. BLINDING

All subjects, Investigators and their staff (except unblinded pharmacist or designated site staff), and all Sponsor/CRO personnel involved in the management of the study will be blinded to treatment assignments.

The Information Technology department will be unblinded to treatment. As noted above, the Technology department is not otherwise involved with the study.

CONFIDENTIAL Page 79 of 108

Treatment unblinding for the study will occur after all clinical data have been received, data inconsistencies have been resolved, and the database is locked, except for safety reasons on a case-by-case basis (i.e., emergency unblinding).

The process for emergency unblinding will be outlined in details in the Randomization Plan. In addition, any subject that is unblinded for any reason will be identified and discussed in the final clinical study report.

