12. DATA SAFETY MONITORING COMMITTEE (DSMC)

A Data Safety and Monitoring Committee (DSMC), independent of the study operations will be established to consider safety data generated during the study and to make recommendations about IA data for sample size re-estimation once 50% of enrolled patients have been in the study for at least 4 weeks after randomization or are withdrawn from the study, whichever occurs first. The details of the DSMC responsibilities will be included in the DSMC charter. The DSMC charter will be developed and operated in adherence to the current FDA guidance on DSMC (Establishment and Operation of Clinical Trial Data Safety Monitoring Committees [March 2006]). The DSMC meetings will take place at least once after the IA, and at other time-points as determined by the DSMC charter. In addition to the pre-specified time-points, the DSMC may also decide to schedule a meeting whenever they decide a review of emergent safety data is warranted. The charter will detail the roles and responsibilities of the DSMC members once they have been appointed. The study data will be provided to the Committee members in the form of a data report. Meetings to discuss the data will be held in person or by teleconference, based on the DSMC Chair's decision. The meetings will be in two stages: an "open stage" which will involve discussion on general aspects of the trial, and a "closed stage" between the DSMC members only. The remit of the DSMC will be primarily to assess the safety aspects of the trial.

CONFIDENTIAL Page 94 of 108

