#### 5.1.6 Stopping Rule

There is no intention of stopping the study as a result of this safety analysis. However, DSMC may recommend stopping the trial for safety reasons at any time.

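### Protocol 5.2 lets the medical monitor and the Sponsor allow the study to proceed after a safety stopping criterion is met, with no required review by the independent DSMC

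*Protocol*

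**What the plan says.** Protocol 5.2 lists four kinds of trigger event, all of which depend on attribution to study drug. When one occurs:

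- **Review:** "data will be reviewed by the Medical Monitor and the Lead Principal Investigator".
- **Immediate action:** "patient accrual will be suspended pending further review and the FDA and other global regulatory authority will be notified".
- **Default and exception:** the study stops "unless, after reviewing the safety events of interest, the medical monitor and Sponsor, agree to allow the study to proceed".
- **Regulators before restart:** "The FDA and other global regulatory authority will be consulted for any protocol amendment before restarting the trial if a stopping rule is met".

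The DSMC is not mentioned in 5.2.

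Elsewhere the plan sets up such a committee. Protocol Section 12 describes it as "independent of the study operations will be established to consider safety data generated during the study" and adds: "The remit of the DSMC will be primarily to assess the safety aspects of the trial". It may call its own meetings, and its detailed duties are left to a charter. SAP 5.1.2 and 5.1.4 give it unblinded data prepared by an independent statistician. SAP 5.1.6 says that the "DSMC may recommend stopping the trial for safety reasons at any time".

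On blinding, Protocol 8.6 states that "all Sponsor/CRO personnel involved in the management of the study will be blinded to treatment assignments".

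**The concern.** A met stopping criterion is the point in a trial where independent judgement on safety is most useful. Here the decision to carry on belongs to two parties. One is the Sponsor, which has an interest in continuing. In the randomized phase the Sponsor is also blinded, so it would weigh a possible drug-related death or life-threatening event without knowing which arm it came from. A body that is independent and can see allocation already exists, but the rule does not require anyone to tell it or ask it.

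What is at stake is the reliability of the restart decision. Without knowledge of allocation, a true signal on leronlimab and an event on placebo that was attributed to study drug can look alike.

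Section 5.2 also names two different pairs. The Lead Principal Investigator reviews but does not decide. The Sponsor decides but is not among the named reviewers.

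**Working it through.** No arithmetic applies: the question is who decides and with what information. The check sets the relevant sections side by side.

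**1. Who acts after a trigger (Protocol 5.2).** The reviewers are the Medical Monitor and the Lead Principal Investigator. Those who may let the study proceed are the medical monitor and the Sponsor. The section does not say who carries out the further review during the suspension, beyond these roles.

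**2. Whether another section brings in the DSMC.**

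- Protocol 9.4 sends serious adverse events to the Medical Monitor within 24 hours and states no onward route to the DSMC.
- Protocol 12 lets the DSMC meet when it sees a need, at its own discretion. It does not link this to a 5.2 trigger.
- Protocol 1.6 says the board will be alerted to the risk of West Nile infection. That is a different matter.
- SAP 5.1.6 lets the DSMC recommend stopping at any time. It does not say that the DSMC is told of a trigger.

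No section sends a 5.2 trigger to the DSMC or makes its view a condition of restart.

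**3. What those deciding can see, randomized subjects.** Protocol 8.6 and SAP 2.6 blind Sponsor and CRO staff who manage the study. The contact block in Protocol 9.4 places the Medical Monitor in the CRO's safety department, so the general rule appears to cover that role. This is an inference. Protocol 8.7.2 lets the Medical Monitor, in consultation with the sponsor, decide on emergency unblinding, and does not say whether the Medical Monitor then learns the allocation. Investigators are blinded too, so the attribution that sets off a trigger is made without knowledge of the arm.

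**4. What those deciding can see, open-label subjects.** Everyone receives leronlimab, so blinding is not an issue. Independence still is. The Sponsor shares the restart decision, and under Protocol 8.3 enrollment stays open until the Sponsor and/or FDA closes it.

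**5. Whether scheduled DSMC looks fill the gap.** SAP 5.1.1 sets safety looks when about 100 and about 300 subjects have completed two weeks of randomized treatment or withdrawn. SAP 5.2 sets the interim analysis at about 195 subjects after four weeks of randomized treatment or withdrawal. All three are defined by randomized treatment. None is set off by a 5.2 event, and none is defined by open-label enrollment.

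**6. Whether the regulator step fills the gap.** Notification is required at the trigger. Consultation before restart is worded around a protocol amendment. If no amendment is made, it is unclear whether any consultation is needed. Neither step requires independent review of unblinded data.

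**The case against.** The best case for the plan has five parts.

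- **The default is cautious.** Accrual is suspended, regulators are told, and the study stops unless there is agreement to continue. This stands, and it means the decision is not unchecked.
- **The DSMC can act by itself.** It may meet when it wishes and recommend stopping at any time. This also stands, but it depends on the DSMC learning of the event.
- **The charter may cover this.** It may: the charter is not among the documents. Section 5.2 does not refer to it, however, and 5.2 is the text that sites and ethics committees read.
- **The two pairs in 5.2 may be sequential roles, and an advisory DSMC is a legitimate choice.** Both are fair. The wording is therefore unclear rather than contradictory, and the proposal below keeps the DSMC advisory.
- **This protocol version adds an open-label phase after randomized enrollment is complete.** For open-label events a comparison by arm adds nothing. This is correct and limits the blinding argument to randomized subjects.

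A reader might also infer more than the documents support:

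- *That the expected number of deaths, or the 2:1 allocation, measures the problem.* The triggers need attribution to study drug, so all-cause mortality does not show how often 5.2 would apply. The allocation ratio does not measure the effect of leaving the DSMC out.
- *That about 100 subjects could be enrolled between DSMC looks after a criterion is set aside.* This ignores ad hoc meetings and the completion of randomized enrollment.
- *That 5.2 would draw the Sponsor into unblinding.* Section 5.2 says nothing about unblinding. For unblinded regulatory reporting, Protocol 8.7.2 uses unrelated staff and keeps allocation from study personnel.

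**Conclusion.** The point holds as a gap in safety governance. As written, a met stopping criterion can be set aside by the medical monitor and the Sponsor without any required input from the DSMC, the body that the plan itself makes independent and gives unblinded data. The existing safeguards reduce the gap but do not close it, because none requires independent review before restart.

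The documents give no basis for a numerical size. The power calculation and the primary analysis are not touched. This is a cheap and worthwhile improvement, not a defect that undermines the trial.

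The conclusion rests on three assumptions:

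- the unseen charter does not already require that triggers go to the DSMC;
- the medical monitor is blinded for randomized subjects, which is inferred from the CRO role;
- 5.2 also governs the open-label phase, since nothing in it limits it to randomized subjects.

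If the charter does contain such a requirement, what remains is a missing cross-reference in 5.2. If the medical monitor does know allocation, the blinding argument is weaker for that role, but the lack of independent review remains.

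**What to change.** In Protocol 5.2, with matching text in the DSMC charter:

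1. Require that the DSMC be notified promptly whenever any listed criterion is met.
2. Require an ad hoc DSMC review of the relevant safety data. For randomized subjects this would be by arm, prepared by the independent statistician behind the existing firewall. For open-label subjects it would be the single-arm data.
3. Require the DSMC's written recommendation before the Sponsor decides whether the study proceeds.
4. Reconcile the two sets of people named in 5.2, stating who reviews, who recommends and who decides.

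Leave the event criteria unchanged. They are a clinical matter and are not in question here.

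The cost is one paragraph in 5.2 and a charter entry. The DSMC, the independent statistician, the firewall and the provision for ad hoc meetings are already in the plan. The downside is that resuming accrual may take a few days longer.
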